### **8.5.4 Subgroup Analysis**

Given the small sample size in this study, no subgroup analyses will be performed.

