7.5. SUBGROUP ANALYSES

No subgroup analyses will be performed for this study.

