15.3.3.2. ANALYSIS

Observed and change values will be summarized by treatment group. Means with 95% CI will be plotted for Observed and CFB values over time with treatment groups overlaid. Individual values over time will be plotted over time per treatment group.

An analysis of covariance model will be fit for CFB/CFEOT at each scheduled time, with a fixed effect for treatment group and a covariate for the baseline value. Comparisons will be made between each dose level, and all active treated subjects combined versus placebo at the 5% significance level (two-sided). Least-squares treatment means and mean differences will be estimated with 95% CI and two-sided p-values for the test of no treatment difference.

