15.3.18.2. ANALYSIS

Shift tables will be presented, tabulating the number of subjects moving from baseline to the each of the result categories for these laboratory tests. This analysis may be repeated for subjects assessed with active renal disease at any point during the trial, if sufficient sample size is available.

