15.3.19.2. ANALYSIS

The analyses will replicate those performed for CLASI. This analysis will be repeated for subjects assessed with active renal disease at any point during the trial.

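### SAP 15.3.19.2 orders a five-group ANCOVA with p-values in a renal subset that is defined after randomisation and probably too thin, although both documents rule out subgroup analyses

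*SAP*

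**What the plan says.** SAP 15.3.19.2 covers protein/creatinine ratio and eGFR: "The analyses will replicate those performed for CLASI". It continues: "This analysis will be repeated for subjects assessed with active renal disease at any point during the trial".

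The CLASI analysis (SAP 15.3.3.2) is an ANCOVA at each scheduled time, "with a fixed effect for treatment group and a covariate for the baseline value". Each dose, and all active subjects combined, is compared with placebo at a two-sided 5% level. The output is least-squares means and differences, with "95% CI and two-sided p-values for the test of no treatment difference". SAP 6.1 pools the placebo subjects, so there are five groups.

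On subgroups, SAP 7.5 states: "No subgroup analyses will be performed for this study". Protocol 8.5.4 states: "Given the small sample size in this study, no subgroup analyses will be performed". The adjacent SAP section on urinary casts, pyuria and hematuria (15.3.18.2) uses shift tables only, and allows their repeat in the same renal subset only "if sufficient sample size is available".

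The protocol bears on this in two further places. Section 6.2.3.3 lists proteinuria and eGFR changes in subjects who have active renal disease at baseline among the exploratory outcomes. Section 8.5.3 assigns ANCOVA, each dose and overall against placebo, to continuous exploratory endpoints based on change from baseline. SAP 3.4 reports no meaningful deviation from the protocol's analyses.

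**The concern.** There are three linked problems.

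First, the instructions conflict. A programmer cannot follow both SAP 7.5 and SAP 15.3.19.2. The renal analysis with formal tests carries no size condition, while the simpler shift tables next to it do.

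Second, the subset has changed. The protocol fixes it by status at baseline. The SAP admits anyone assessed with active renal disease at any time in the trial. SAP 15.3.11 analyses the occurrence of active renal disease, and the time to it, as outcomes. Membership can therefore depend on something that treatment may affect, and a comparison of doses with placebo inside that subset is no longer protected by randomisation, whatever its size.

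Third, the subset may be too small for the model. Enrolment is irrespective of organ involvement (protocol 2.4), with no renal quota, and each group has 8 subjects. Followed as written, the plan could report differences, intervals and p-values that rest on one or two subjects per side, or that cannot be estimated.

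**Working it through.** **Inputs.** Protocol 5.3 gives 10 subjects per cohort at 4:1. That is 10 × 4/5 = 8 active per dose, and 4 cohorts × 2 = 8 placebo, pooled. Five groups of 8 make 40, which reproduces the planned numbers. The sample size rests on clinical judgment (protocol 8.1, SAP 3.1.1), so there is no power figure to reproduce. The share q of subjects with active renal disease is not in the documents. It is assumed to be 10 to 40%, the same in every group and independent between subjects.

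**Model size.** Five group means plus one baseline slope make 6 parameters. With all five groups filled, residual df = n − 6, so at least 7 renal subjects are needed for 1 df.

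**Filling the groups.**

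- P(a given group is empty) = (1 − q)^8, and P(at least one of five is empty) = 1 − [1 − (1 − q)^8]^5.
- P(a given group has 0 or 1) = a = (1 − q)^8 + 8q(1 − q)^7, and P(at least one such group) = 1 − (1 − a)^5.

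At q = 20%, 0.8^8 = 0.168 and 1 − 0.832^5 = 0.60. Then a = 0.168 + 0.336 = 0.503 after rounding, and 1 − 0.497^5 = 0.97.

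**Precision.** With m = 8q per group, the smallest dose-placebo difference that reaches p < 0.05 is t(0.975, df) × √(2/m), in residual SDs. This ignores baseline imbalance.

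- 20%: df = 8 − 6 = 2, and 4.30 × √(2/1.6) = 4.8.
- 30%: df = 12 − 6 = 6, and 2.45 × √(2/2.4) = 2.2.
- 40%: df = 16 − 6 = 10, and 2.23 × √(2/3.2) = 1.8.
- Full set: df = 40 − 6 = 34, and 2.03 × √(2/8) = 1.0.

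| Assumed share | Expected renal subjects (per group) | P(at least one empty group) | P(at least one group with 0 or 1) | P(placebo has 0 or 1) | Difference for p < 0.05 |
|---|---|---|---|---|---|
| 10% | 4 (0.8) | 94% | >99% | 81% | none: 4 subjects, 6 parameters |
| 20% | 8 (1.6) | 60% | 97% | 50% | 4.8 SD |
| 30% | 12 (2.4) | 26% | 77% | 26% | 2.2 SD |
| 40% | 16 (3.2) | 8% | 43% | 11% | 1.8 SD |
| Full set | 40 (8) | – | – | – | 1.0 SD |

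The last column assumes all five groups are filled at their expected size. At 20% that is not the typical trial, because a group is empty in 60% of them. The placebo column matters most, since all five contrasts use placebo.

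**Whole-number cases.** With exactly 2 per group (df 4), the 95% CI half-width for one dose against placebo is 2.8 SD and power for a 1 SD difference is 12%. With 4 per group (df 14) the figures are 1.5 SD and 26%. With the full 8 per group they are 1.0 SD and 49%.

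**Outside the assumed range.** At a 50% share, P(an empty group) falls to 2%, and all five groups have 2 or more with probability 84%. An 80% chance of no empty group needs a share of about 32%. An 80% chance of 2 or more in every group needs about 48%. If enrolment reached 60, assumed evenly split at 12 per group, P(an empty group) at a 20% share would still be 1 − (1 − 0.8^12)^5 = 30%.

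**Volume of tests.** If all protocol visit days are analysed, the subset yields 2 variables × (6 days of change from baseline + 2 days of change from end of treatment) × 5 contrasts = 80 nominal p-values.

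**The case against.** The strongest defence is that the SAP follows the protocol. Protocol 6.2.3.3 names the renal subset and protocol 8.5.3 prescribes ANCOVA for exploratory change endpoints, so the SAP neither invents the subset nor exceeds the protocol's general method. A named exploratory endpoint can also be read as a specific provision beside a general ban. The first part stands: the conflict is also inside the protocol, where 6.2.3.3 and 8.5.3 pull against 8.5.4. A reader might infer from the mean-and-median wording of 6.2.3.3 that the protocol wanted only descriptive statistics here. That does not follow, because the same wording covers SLEDAI, CLASI and other endpoints that fall under 8.5.3.

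Other strong readings also go beyond the documents:

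- That the groups cannot be filled. This depends on a share that nobody states, and at 40 or 50% an empty group is unlikely.
- That both documents exclude subgroups because of small size. Only the protocol gives that reason.
- That the entry limits on creatinine and eGFR keep renal subjects out. Protocol 6.2.2 defines active renal disease by urinary protein and sediment, or by isolated severe proteinuria, so eligible patients can meet it.
- That renal results will steer a nephritis study. Protocol 2.4 says only that the study's preliminary findings may help guide later studies, with nephritis as an example.

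Finally, the p-values are nominal, SAP 7.4 calls the study hypothesis generating, and a contrast that cannot be estimated would be visible as such. That limits the harm. It does not remove the contradiction, and it does not answer the change in the subset's definition.

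**Conclusion.** The point holds as a minor one. SAP 15.3.19.2 unconditionally requires a model-based subset analysis that SAP 7.5 and protocol 8.5.4 exclude. It lacks the size condition of SAP 15.3.18.2, and it replaces the protocol's baseline subset with one that can be determined after randomisation. The conflict and the changed definition are plain from the text and need no assumption.

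The size of the thin-data problem does rest on an assumption, the renal share. Up to about 30%, at least one group with 0 or 1 subject is the likely result (77% or more). At 40% it is still close to even (43%). Where the groups are filled, the dose contrasts detect only differences of about 1.8 SD or more at shares up to 40%. The supportable statement is that the groups are unlikely to be adequately filled unless the renal share is high, and that the contrasts are imprecise even when they are. The primary safety objective and the SRI endpoint are not affected.

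**What to change.** In SAP 15.3.19.2:

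- Define the subset as in protocol 6.2.3.3, by active renal disease at baseline. SAP 15.3.18.2 uses the same any-time wording and should be aligned.
- Replace the subset ANCOVA, intervals and p-values with descriptive statistics (n, mean and median of observed values, change and percentage change) for each dose, all active and placebo, plus a subject listing.

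Elsewhere in the SAP:

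- In 7.5, name the renal subset as the one exception, and reconcile this with protocol 8.5.4.
- In 3.4, record that the ANCOVA of protocol 8.5.3 is not applied in this subset.

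The cost is SAP wording, with less programming. The baseline definition can only keep the subset the same size or make it smaller, which is a further reason for a descriptive display. What is lost is a set of nominal p-values, up to 80, that would be non-estimable or nearly uninformative unless the renal share turned out to be high.

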16. PHARMACOKINETIC OUTCOMES

16.1. PHARMACOKINETIC CONCENTRATIONS

Concentrations of brentuximab vedotin (ADC), total antibody (TAb), and monomethyl auristatin E (MMAE) will be assayed for samples collected on Days 1, 2, 3, 8, 15, 22, 43, 64, 85 and 106. Antitherapeutic antibodies are measured prior to each dosing and on Days 1, 85, 106, and 127.

16.2. PHARMACOKINETIC PARAMETERS

Derivation the pharmacokinetic parameters is the responsibility of the sponsor or designee, and outside the scope of this SAP.

16.3. ANALYSES

A listing of PK blood sample collection times as well as derived sampling time deviations will be provided.

Plasma concentrations will be summarized using descriptive statistics for each treatment group/dose level. Concentrations that are below the limit of quantitation (BLQ) will be treated as zero for the computation of descriptive statistics. Figures of arithmetic mean concentration-time data \pm SD will be presented for each treatment on linear and semi-logarithmic scales. The incidence of antitherapeutic antibodies will be tabulated.

A subject listing of all concentration-time data for each treatment will be presented. Individual subject concentration-time data will be graphically presented on linear and semi-logarithmic scales.

Plasma parameters will be summarized using descriptive statistics for each treatment group/dose level. Dose proportionality will be assessed using least-squares regression of the log-transform PK parameters on log dose. Slope and intercept estimates will be presented with 90% CI. AUC and Cmax parameters will be plotted vs dose on the log-log scale, with the regression lines overlain.

17. PHARMACODYNAMIC OUTCOMES

17.1. PHARMACODYNAMIC VARIABLES

The following variables are collected as PD endpoints throughout this study:

Document: SGN35-022 SAP v1 V0.3
Author: [REDACTED]

Version Number: 1.0
Version Date: 31Jan2017

Template No: CS_TP_BS016 – Revision 3
Effective Date: 01Apr2016

Reference: CS_WI_BS005

[REDACTED]

- flow cytometry for specific lymphocyte populations
- inflammatory markers, including: ESR, hsCRP, sCD30, and soluble CD153 (sCD153)
- quantitative autoantibody assays including, but not limited to:
 - antinuclear antibodies (ANA), as assessed by indirect immunofluorescence titer: quantified in ratios such as 1:80, 1:160, 1:320.
 - anti-dsDNA;
 - anti-C1q (quantitative);
 - anti-Smith antibodies (anti-Sm), anti-ribonucleoprotein (anti-RNP), anti-Sjögren's Syndrome A antibodies (anti-SSA), and anti-Sjögren's Syndrome B antibodies (anti-SSB);
 - anti-cardiolipin IgA, IgG and IgM, anti-β-2-glycoprotein IgG and IgM, lupus anticoagulant;
 - direct Coombs test (Positive/Negative); and
 - quantitative IgG, IgM, IgA, and IgE
- complement studies: C1q, C3, C4, and CH50
- lymph node or tonsil biopsies (optional): T cell subpopulations, CD4+ and CD4+CD30+, and subpopulations of each, CD8+ and CD8+CD30+; B cell subpopulations, germinal center structure

Note that samples collected for cytokine assessment were planned for possible future testing and therefore outside the scope of this SAP.

17.2. DERIVATIONS

CFB, PCFB, CFEOT and PCFEOT will be calculated for all quantitative PD tests. The following reductions in PCFB from baseline will be derived for ESR only: 20%, 50% and 70% (ESR20/50/70).

17.3. ANALYSES

The analyses for all PD variables scores will replicate those performed for CLASI. ESR20/50/70 will be tabulated by treatment. The incidence of positivity for the following will also be tabulated: ANA, anti-dsDNA, anti-Sm, anti-RNP, anti-SSA, anti-SSB, anti-cardiolipin, anti-β-2-glycoprotein I, lupus anticoagulant, anti-C1q, and direct Coombs test.

Assayed values reported by the labs as below limit of quantitation (BLQ: e.g. <0.3 U/mL) will be treated as that limit for analyses. For summarizing incidence, BLQ values will be treated as Negative.

The following tests will be analyzed on the log 10 scale: anti-SSA, anti-SSB, anti-RNP70.

For ANA values, the denominator will be used for analyses (e.g. 80, 160, 320) and log-transformed for quantitative analyses.

Any results from lymph node or tonsil biopsies will be listed only.

18. PHARMACOKINETIC/PHARMACODYNAMIC ANALYSES

PK vs PD analyses are outside the scope of this document and may be analyzed separately.

19. SAFETY OUTCOMES

All analyses for safety outcomes will be based on the Safety Analysis Set.

The assessment of safety during the course of this study will consist of the surveillance and recording of AEs, including SAEs; recording of concomitant medications; physical and neurological examination findings; ECG recordings; and measurements of vital signs and protocol-specified laboratory tests. In addition, subjects will be closely monitored for signs and symptoms suggestive of neuropathy or PML.

19.1. ADVERSE EVENTS

An AE is any untoward medical occurrence in a patient or clinical investigational subject administered a medicinal product and which does not necessarily have a causal relationship with this treatment

Adverse Events (AEs) will be coded using MedDRA central coding dictionary, Version 18.0.

Treatment emergent adverse events (TEAEs) are defined as AEs that started or worsened in severity on or after the first dose of study medication.

Pretreatment AEs are defined as AEs occurring prior to dosing. These events will be presented in the listings only and are not included in the tabular summary of AEs.

See Appendix 2 for handling of partial dates for AEs. In the rare case where it is not possible to assess treatment emergence, the AE will be classified as treatment emergent (i.e. the worst case).

Severity

Adverse event severity will be graded using the NCI-CTCAE, version 4.03. TEAEs starting after the first dose of study medication with a missing severity will be classified as severe. If a subject reports a TEAE more than once within that SOC/ PT, the AE with the worst case severity grade will be used in the corresponding severity summaries.

Relationship to Study Medication

Relationship to study medication, as indicated by the Investigator, is classified as Related and Unrelated .A "related" TEAE is defined as a TEAE with a causal relationship between the study drug and the AE, such as:

- an event that is uncommon and known to be strongly associated with drug exposure (eg, angioedema, hepatic injury, or Stevens-Johnson syndrome); or
- an event that is not commonly associated with study drug exposure, but is otherwise uncommon in the population exposed to the drug (eg, tendon rupture).

An unrelated AE to study medication is defined as another cause of the AE is more plausible (eg, due to underlying disease or occurs commonly in the study population), or a temporal sequence cannot be established with the onset of the AE and administration of the study drug, or a causal relationship is considered biologically implausible.

TEAEs with a missing relationship to study medication will be regarded as "related" to study medication. If a subject reports the same AE more than once within a particular SOC/ PT, the AE with the highest level of relationship to study medication will be used in the corresponding relationship summaries.

All AE tabulations will be performed by treatment group and active-treated overall, and will include the number and percentage of subjects. All percentages will be based on the number of patients in the Safety Population. Incidence of TEAEs will be tabulated by the following:

- Across all System Organ Class (SOC) and Preferred Term (PT), By Severity Grade, by Relationship, by Leading to Discontinuation, and by Seriousness
- By System Organ Class (SOC) and Preferred Term (PT)
- By System Organ Class (SOC), Preferred Term (PT) and Severity Grade
- By System Organ Class (SOC), Preferred Term (PT) for AEs Related to study medication only

19.1.1. TEAEs LEADING TO DISCONTINUATION OF STUDY MEDICATION

TEAEs leading to permanent discontinuation of study medication or dose interruption will be identified by using the variable pertaining to outcome on the Adverse Events page of the CRF, and listed.

19.1.2. SERIOUS ADVERSE EVENTS

Serious adverse events (SAEs) are those events recorded as "Serious" on the Adverse Events page of the CRF, and will be summarized and listed.

Incidence of serious TEAEs will be tabulated by the following:

- By System Organ Class (SOC) and Preferred Term (PT)
- By System Organ Class (SOC), Preferred Term (PT) and Severity Grade
- By System Organ Class (SOC), Preferred Term (PT) and Severity Grade for SAEs Related to study medication only

19.1.3. ADVERSE EVENTS OF SPECIAL INTEREST

AEs of special interest (AEOSI) are defined as those related to peripheral neuropathy (including PML) and infusion site reactions (eg, pain, irritation, itching), and will be identified using the corresponding standardized MedDRA query. AEOSI will be separately listed and summarized by SOC/PT and overall.

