#### **Safety**

**Adverse Events:** Adverse events will be coded using the Medical Dictionary for Regulatory Activities and will be summarized by presenting the number and percentage of subjects having any AE, having an AE in each system organ class, and having each individual AE as reported by preferred term. Furthermore, a summary for serious AEs and summaries by severity (according to the National Cancer Institute's Common Terminology Criteria for Adverse Events, version 4.03) and relationship to study drug will be presented. Most frequent AEs and drug-related AEs will also be provided. In addition, AEs of special interest (including, but may not be limited to, PML and neuropathy) will be summarized.

Subject death due to any cause and subjects with AEs leading to study drug discontinuation will be listed and summarized.

Proportion of subjects who discontinue study drug or dose interruption due to treatment-emergent AEs will be summarized by treatment.

**Laboratory values:** Laboratory data will be summarized as mean change from baseline to endpoint. Shift tables will also be produced describing changes from normal to abnormal (high and low) levels or abnormal (high and low) to normal levels.

**Vital Signs, Physical Findings, and Other Safety Evaluations:** Vital signs will be listed and summarized over time by treatment and overall. Changes from baseline will also be summarized. Notable values and changes will be tabulated.

Electrocardiogram evaluations will be summarized by treatment and visit.

Individual listings presenting subjects with flags will be created for both changes and absolute values.

Physical and neurological examination findings will be displayed in a descriptive manner for each subject.

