2 were unable to be adjudicated. This corresponds to a rate (0.048%) not higher than the published background rate of PML in patients with lymphoproliferative disorders treated with chemotherapy (0.07% to 0.52%). Studies on the risk of PML with other therapies, specifically natalizumab, indicate that the risk of PML is primarily increased in patients treated continuously for prolonged periods, ie, more than 12 months, and in subjects known to be seropositive for John Cunningham virus (JCV) antibody. The present study is limited to 4 doses of brentuximab vedotin administered over 12 weeks, and will test all subjects for JCV seropositivity at screening. These results will be available to the Investigator and subject before randomization to facilitate an informed decision to proceed in the study. During the study, a clinical monitoring plan for PML, including neurological examinations, will be implemented to monitor closely for signs and symptoms suggestive of PML, which may include altered mental status, motor deficits such as hemiparesis or ataxia, visual disturbances, or higher cortical dysfunction such as dysphasia or agnosia, or seizures, which may occur over weeks to months.

Other warnings and precautions for the use of brentuximab vedotin, which are pertinent to a population of patients with SLE, include infusion-related reactions (including anaphylaxis), serious and opportunistic infections, Stevens-Johnson syndrome, and embryo-fetal toxicity. All doses of study drug will be administered in the clinic by appropriately trained personnel and women who are pregnant are not allowed to participate in the study. In this study, subjects will be closely monitored throughout the study for the emergence of signs or symptoms suggestive of infection or other conditions of concern.

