### **Adverse Events of Special Interest**

For this study, AEs of special interest include any treatment-emergent neuropathy and suspected cases of PML (see Section [6.3.1.3](#) for reporting of AEs). These events will be followed until significant changes return to baseline, the event stabilizes or is no longer considered clinically significant by the Investigator, the subject dies or withdraws consent, or the study is closed.

Subjects who experience a Grade 2 neuropathy will have dosing withheld (see Section [5.1](#)); subjects with Grade 3 or higher neuropathy will be withdrawn from the study (see Section [4.4.4](#)).

See Section [6.3.3](#) for additional information on PML monitoring and Section [6.3.2](#) for management of infusion reactions.

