#### **Diagnosis Versus Signs or Symptoms**

In general, the use of a unifying diagnosis is preferred to the listing out of individual symptoms. Grouping of symptoms into a diagnosis should only be done if each component sign and/or symptom is a medically confirmed component of a diagnosis as evidenced by standard medical textbooks. If any aspect of a sign or symptom does not fit into a classic pattern of the diagnosis, report the individual symptom as a separate AE.

Important exceptions for this study are adverse reactions associated with the infusion of study drug. For infusion-related reactions, do not use the NCI-CTCAE terms of 'cytokine release syndrome,' 'acute infusion reaction,' or 'allergic or hypersensitivity reaction.' Instead, record each sign or symptom as an individual AE. If multiple signs or symptoms

occur with a given infusion-related event, each sign or symptom should be recorded separately with its level of severity.

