### **6.3.2 Management of Infusion Reactions**

Infusion-related reactions may occur during the infusion of study treatment. The infusion should be administered at a site properly equipped and staffed to manage anaphylaxis should it occur. All supportive measures consistent with optimal subject care should be given throughout the study according to institutional standards. Supportive measures may include administering medications for infusion-related reactions.

Subjects who have experienced a Grade 1 or Grade 2 infusion-related reaction should be premedicated for subsequent infusions. Premedication may include acetaminophen and an antihistamine administered 30 to 60 minutes prior to each brentuximab vedotin infusion or according to institutional standards.

If anaphylaxis occurs, brentuximab vedotin administration should be immediately and permanently discontinued.

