### **6.3.3 Progressive Multifocal Leukoencephalopathy Assessment**

Study site personnel and subjects will be educated regarding the signs and symptoms of PML. Close monitoring during the course of the study for any new symptoms or signs suggestive of PML will be performed, with regular neurologic examinations (including evaluation of cranial nerves, motor and sensory function, coordination, and mental status). The PML assessment will be conducted by a qualified individual and will be performed at screening and as indicated on the schedule of events (see [Table 3](#)).

If a subject has a positive finding on the PML assessment or if there is strong clinical suspicion for PML, the event should be expeditiously reported as an AE of special interest within 24 hours (see Section [6.3.1.4](#)). If PML is suspected, dosing with study drug for that subject will be suspended and the subject should be promptly referred to a neurologist. Following formal evaluation by a neurologist, further work up will include brain magnetic resonance imaging performed with and without contrast. If PML cannot be ruled out, a

lumbar puncture with cerebrospinal fluid analysis for JCV by polymerase chain reaction may be performed. If JCV is detected, the subject should be treated as a PML case, permanently discontinue study drug, and transfer to safety follow-up. Dosing with study drug can only be resumed in subjects where PML has been ruled out.

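### SAP 19.1.3 places PML inside peripheral neuropathy with no rule for suspected cases, and the SAP's treatment-emergence date table has no branch for worsening

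*SAP*

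**What the plan says.** **Special-interest definition.** SAP 19.1.3 states: "AEs of special interest (AEOSI) are defined as those related to peripheral neuropathy (including PML) and infusion site reactions (eg, pain, irritation, itching". Membership is decided by the matching standardized MedDRA query, which is not named. The events are then listed and summarized by system organ class, preferred term and overall.

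Protocol 6.3.1.1 states: "AEs of special interest include any treatment-emergent neuropathy and suspected cases of PML". The same pairing of neuropathy and suspected PML appears in that section's rule on recording adverse events and again in 6.3.1.3. Under Protocol 6.3.3, after a positive PML assessment or on strong clinical suspicion, "the event should be expeditiously reported as an AE of special interest within 24 hours". The synopsis is looser: "AEs of special interest (including, but may not be limited to, PML and neuropathy) will be summarized". It omits the word *suspected*, keeps the two conditions apart, and leaves the list open.

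**Treatment emergence.** The text of SAP 19.1 counts an event that began, or became more severe, on or after first dose. Pretreatment events go to listings only. The algorithm in SAP Appendix 1, under the partial-date heading, decides on start and stop dates alone.

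**Infusion reactions.** Protocol 2.6 names "infusion-related reactions (including anaphylaxis), serious and opportunistic infections" among the relevant warnings, and 6.3.2 begins: "Infusion-related reactions may occur during the infusion of study treatment". Protocol 6.3.1.2 bars umbrella terms for these reactions: "Instead, record each sign or symptom as an individual AE".

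SAP 3.4 reports no meaningful departure from the protocol's analyses.

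**The concern.** Safety and tolerability is the primary objective, so the special-interest and treatment-emergent counts by arm are main outputs of the trial. PML is a central nervous system disease. Protocol 2.6 describes it by signs such as "altered mental status, motor deficits such as hemiparesis or ataxia, visual disturbances". A rule built on peripheral neuropathy terms has no evident route to a case coded to one of those signs, and suspicion alone is what the protocol says makes the case of special interest.

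The date table raises a similar problem. If it is programmed as written, an event that is mild before Day 1 and severe afterwards could be left out of every treatment-emergent table. Dose groups are small: with 8 planned subjects per dose, one subject classified differently moves an incidence by 1/8 = 12.5 percentage points.

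**Working it through.** **1. PML: following a suspected case through both documents.** A site suspects PML and reports it within 24 hours as an event of special interest (Protocol 6.3.3, 6.3.1.4). Suppose the event is coded to a sign, for example hemiparesis. Under the protocol it is of special interest because it was suspected. Under SAP 19.1.3 it counts only if the unnamed query contains that term. The SAP has no step that brings the site's report into the special-interest group.

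**2. How many such cases to expect.** Protocol 2.6 gives 7 reported cases in 14,614 treated oncology patients: 3 confirmed, 2 judged not PML, 2 not adjudicable. This counts reports, not confirmed cases, so it is the closest available proxy for suspicion.

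- Rate: 7 / 14,614 = 0.048%, matching the protocol's figure.
- Planned active subjects, 4 × 8 = 32: 32 × 7 / 14,614 = 0.015 expected cases.
- If all 60 subjects are enrolled and 4:1 holds, 48 active: 48 × 7 / 14,614 = 0.023.

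The documents give no rate of site-level suspicion in lupus, where neuropsychiatric disease could prompt more.

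**3. The date table, row by row.** There are 4 start-date classes × 3 stop-date classes = 12 rows.

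| Start date | Rows | Result for a pre-dose start |
|---|---|---|
| Known | 3 | Not treatment-emergent |
| Partial, cannot be on or after first dose | 3 | Not treatment-emergent |
| Partial, could be on or after first dose | 3 | Decided on stop date, or assumed emergent |
| Missing | 3 | Decided on stop date, or assumed emergent |

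So 3 + 3 = 6 of 12 rows reject a pre-dose start, and none tests severity. Example: Grade 1 before Day 1, Grade 3 on Day 15, one record. The SAP 19.1 text makes it treatment-emergent; the table does not. Pre-dose records are to be expected, since collection starts at consent (Protocol 6.3.1.3). Protocol 6.3.1.1 requires severity changes to be recorded but does not say whether as a new record. The fields listed in 6.3.1.2 include onset and resolution dates and severity, but no date of grade change.

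**4. Infusion reactions: would a date-window count work?** Label data are in Protocol Appendix 4, section 6.1.

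- True reactions: 19/160 = 11.9% over a median of 9 cycles (Study 1) and 7 cycles (Study 2); 25/167 = 15.0% over a median of 15 (Study 3). Scaled to 4 doses, assuming an even spread over doses: 11.9% × 4/9 = 5.3%, 11.9% × 4/7 = 6.8%, 15.0% × 4/15 = 4.0%. Crossing the extremes (11.9% × 4/15 and 15.0% × 4/7) widens this to about 3% to 9%.
- Coincidental symptoms: take a window of infusion day plus the next day, 2 × 4 = 8 days, with independent onsets spread evenly over follow-up of T days. The share of subjects with at least one is 1 − exp(−(8/T) × Σ[−ln(1−p)]).
  - Study 1, ten label symptoms (13, 42, 13, 17, 29, 25, 19, 27, 14, 22%), T = 9 × 21 = 189: sum 2.5645, × 8/189 = 0.1085, giving 10.3%. This is too high as a pure coincidence rate, because it includes drug effects and true reactions.
  - Study 3 placebo, the eight symptoms tabulated (5, 8, 6, 8, 16, 16, 8, 7%), T = 15 × 21 = 315: sum 0.7846, × 8/315 = 0.0199, giving 2.0%.

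False positives of about 2% to 10% are therefore comparable with the true reactions. Lupus background rates are not given.

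**The case against.** **PML is not hidden.** An event coded as PML has its own preferred-term row. A suspected case coded to a sign still appears in the tables by system organ class and preferred term (SAP 19.1). It is also covered by 24-hour reporting, the withdrawal list in Protocol 4.4.4 and committee review of neurological events in 4.5. All of this stands. A reader might infer that suspected PML would go unseen; the documents do not support that. Only its place in the special-interest summary is at risk.

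**The synopsis also leaves out *suspected*.** True, so the contrast on that word is with Protocol 6.3.1.1, 6.3.1.3 and 6.3.3. The synopsis still separates the two conditions, and the SAP does not.

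**The *overall* summary.** A reader might take it as one total mixing neuropathy, PML and site events. SAP 19.1 uses the same word for pooled active subjects, so that reading is not established.

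**The date table covers partial dates only.** SAP 7.3 invokes it for missing dates, SAP 19.1 for partial ones, and its heading agrees. The SAP 19.1 text may thus be meant to govern fully dated events. But the table contains known-date rows that give the opposite answer, so the conflict needs settling. Protocol 8.6.1 does not settle it: it concerns events that began during the study, which is not a treatment-emergence rule.

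**Infusion reactions.** A reader might infer that the SAP breaks a protocol commitment. It does not. Protocol 6.3.1.1 does not list these as events of special interest, the synopsis allows added categories, and no passage promises a count of subjects with an infusion-related reaction. The table templates mentioned in SAP 8 are not among the documents and may name the queries.

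**Conclusion.** Two points hold. SAP 19.1.3 does not reproduce the protocol's separate category of suspected PML and gives no rule for a case coded to its signs. The date table contradicts the SAP 19.1 definition for events that worsen after a pre-dose start. The infusion wording is a secondary mismatch: the SAP names local reactions where the protocol's stated concern is systemic ones.

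The size of any miscount cannot be estimated. The PML gap depends on the query's contents and on suspected cases occurring at all; about 0.015 are expected in 32 active subjects if the oncology reporting rate carries over. The worsening gap has an effect only if a worsened event keeps its original record. A demonstrated miscount should not be inferred from either. Minor to should-fix: low expected numbers, but a primary safety objective and a cheap correction.

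**What to change.** Before database lock and unblinding:

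- **(a) Special-interest groups.** Make neuropathy and PML separate groups. Name the neuropathy query. Define the PML group as the PML preferred term plus every case that a site reports as suspected PML, whatever its coded term. Record the changed definition in SAP 3.4.
- **(b) Worsening.** Either state that an event worsening in severity on or after first dose is entered as a new record with its own onset date and is treatment-emergent, or limit the Appendix 1 table to partial or missing dates and let the SAP 19.1 text govern the rest. A branch on grade change is usable only if the case report form holds that date.
- **(c) Optional.** Replace infusion site reactions with infusion-related reactions, using a term list fixed in advance and either restricted to investigator-related events or shown beside that subset. Note that a date-only window will catch coincidental symptoms at a rate that may match the true reactions.

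The cost of (a) and (b) is SAP wording, a named query and some programming, mostly on data already collected. The first option in (b) also needs confirmation that sites enter worsening that way. Option (c) adds noise in all arms and can be left out without weakening the other two.
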